2.4.4 Analyses of efficacy endpoints

All efficacy endpoints will be analyzed based on both the population with Type 2 inflammatory asthma phenotype and patients with baseline blood eosinophils ≥ 0.3 Giga/L populations.

Some selected efficacy endpoints will be also analyzed for full ITT population, as well as the Patients with baseline blood eosinophils ≥ 0.15 Giga/L population, and the patients with baseline FeNO ≥ 20 ppb. For more details, refer to [Appendix M](#).

2.4.4.1 Analysis of primary efficacy endpoint(s)

Primary statistical model and adjustment for covariates

The primary analysis of the annualized rate of severe exacerbation events during the 52-week placebo-controlled treatment period is to assess the efficacy of dupilumab. In this primary approach, for the patients who prematurely discontinue treatment, their off-treatment measurements up to Week 52 or the study withdrawal whichever comes earlier will be included for the analysis. Patients who permanently discontinue the study medication will be asked and encouraged to return to the clinic for all remaining study visits. If a patient stays in study until the end of the 52-week treatment period, all severe exacerbation events that happen up to Visit 28 will be included in the primary analysis, regardless whether the patient is on-treatment or not, and the observation duration is defined as from randomization to Visit 28. If a patient withdraws from the study prior to the end of the 52-week treatment period, all observed severe exacerbation events up to the last contact date will be included in the analysis, and the observation duration is defined as from randomization to the last contact date. No imputation will be performed for the unobserved events that may happen after study discontinuation and up to Week 52. This estimand compares

the rate of severe exacerbation for the patients randomized to the dupilumab and placebo arms, regardless of what treatment patients actually received. It assesses the benefits of the treatment policy or strategy relative to placebo.

The annualized rate of severe exacerbation events as defined in [Section 2.1.3.1](#) will be analyzed using a negative binomial regression model. The analysis for the annualized severe exacerbation rate will be performed in the Type 2 inflammatory asthma phenotype, baseline blood eosinophils ≥ 0.3 Giga/L, baseline blood eosinophils ≥ 0.15 Giga/L, baseline FeNO ≥ 20 ppb and full ITT populations.

When performing the analysis for the annualized severe exacerbation rate in the Type 2 inflammatory asthma phenotype, baseline blood eosinophils ≥ 0.15 Giga/L or full ITT population, the model will include the total number of events that occur during the observation period defined above as the response variable, with the treatment arm, age, baseline weight (≤ 30 kg, >30 kg), region, baseline eosinophil level (<0.3 Giga/L, ≥ 0.3 Giga/L), baseline FeNO level (<20 ppb, ≥ 20 ppb), baseline ICS dose level (medium/high) and number of severe exacerbation events within 1 year prior to the study as covariates. When performing the primary endpoint analysis in the baseline blood eosinophils ≥ 0.3 Giga/L population, the baseline eosinophil level will be removed from the model covariates. When performing the primary endpoint analysis in the baseline FeNO ≥ 20 ppb population, the baseline FeNO level will be removed from the model covariates.

Treatment groups, baseline weight, region, baseline eosinophil level, baseline FeNO level, and baseline ICS dose level will be treated as categorical variables. Age and number of severe exacerbation events within 1 year prior to the study will be treated as continuous variables. Log transformed observation duration will be the offset variable. In the case where the negative binomial regression model may not converge, a categorical variable for the number of severe exacerbation events within 1 year prior to study (1, 2, more than 2) will replace the corresponding continuous variable in the model. A similar approach will also be applied to other analyses for severe exacerbation endpoint if applicable.

Comparisons of the annualized event rates between dupilumab and placebo will be derived by testing dupilumab group versus placebo. The estimated annualized event rate for each treatment group and its two-sided 95% confidence intervals will be derived from the negative binomial model.

Sample SAS code can be found below:

```
proc glimmix data=event;
  class weight eosblgpn1 fenoblgrn ics trt01pn cntygr1n;
  model numevents=trt01pn age weight eosblgpn1 fenoblgrn ics cntygr1n asmanum
    /offset=logdur dist=negbin link=log solution;
run;
```

If the model fails to achieve convergence, different estimation algorithms will be applied following the order: default→LAPLACE→QUAD; if the non-convergence issue still exists, other handling may be considered. The adjustment will be added to the footnote of the corresponding outputs.

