8.4 METHOD OF ASSIGNING PATIENTS TO TREATMENT GROUP

A randomized treatment kit number list will be generated centrally by Sanofi. The investigational product (dupilumab or placebo) will be packaged in accordance with this list.

The Sanofi Clinical Supplies team will provide the randomized treatment kit number list and the Study Biostatistician will provide the randomization scheme to the centralized treatment allocation system (IVRS/IWRS). This centralized treatment allocation system will generate the patient randomization list according to which it will allocate the treatments to the patients.

Patients who meet the entry criteria will be randomized to receive either dupilumab or placebo. Rescreening is not permitted if the patient fails to meet inclusion criteria. Patients who meet exclusion criteria may be rescreened once during the open Screening Period of the study. There is no requirement for a waiting period between the screen-failure date and the rescreening date. The IVRS/IWRS report will flag rescreened patients. Patients that are rescreened must have parent(s)/caregiver(s)/legal guardian(s) resign a new ICF and sign a new IAF, and all Screening Visit 1 procedures must be repeated.

The Investigator obtains treatment kit numbers at randomization and subsequent scheduled visits via an IVRS/IWRS that will be available 24 hours a day.

Patients will be randomized (2:1 ratio) to receive dupilumab or matching placebo. After a patient is randomly assigned to dupilumab or matching placebo, the dosage of dupilumab or matching placebo for the patient, 200 or 100 mg SC once q2w, will be determined based on bw >30 kg or ≤30 kg, respectively.

Randomization will be stratified by ICS dose (medium-dose versus high-dose) and eosinophil count (<300 cells/μL versus ≥300 cells/μL) at Screening, and by region.

A randomized patient is defined as a patient who is registered and assigned with a treatment kit number from the centralized treatment allocation system, as documented from its log file.

A patient cannot be randomized more than once in the study.

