11.4.4.3 Pharmacodynamics and Phenotyping

The values to be used as baselines will be those collected at Visit 2 (Day 1). If any of the scheduled assessments on Day 1 are technically disqualified (eg, insufficient sample), then values determined in any other samples collected prior to the first IMP administration can be used as baseline.

For all parameters, raw data, absolute changes from baseline and percent changes from baseline will be summarized in descriptive statistics by treatment group and time point.

Summary plots (mean \pm SEM) on raw data, absolute changes from baseline and percent changes from baseline will be provided by treatment group.

As part of exploratory analysis, correlations between the baseline values for biomarkers and efficacy endpoints will be assessed.

11.4.5 Analyses of Patient Reported Outcomes (Health-related Quality of Life/Health Economics Variables)

Patient reported outcome variables collected in this study include the ACQ-IA questionnaire ACQ-7 score, PAQLQ(S)-IA score, PACQLQ score, and PRQLQ-IA score (in those with history of allergic rhinitis). The change from baseline for these endpoints will be analyzed using MMRM in the same fashion as for the endpoint of pre-bronchodilator % predicted FEV1. The covariates to be included are treatment, age, weight ($\leq 30\text{kg}$, $>30\text{kg}$), region, baseline eosinophil level ($<300\text{ cells}/\mu\text{L}$, $\geq 300\text{ cells}/\mu\text{L}$), baseline FeNO level ($<20\text{ ppb}$, $\geq 20\text{ ppb}$), baseline ICS dose level (medium/high), visit, treatment-by-visit interaction, corresponding baseline value and baseline-by-visit interaction. Descriptive statistics including number of patients, mean, standard error and LS means will be provided for each timepoint. In addition, differences in LS means, the corresponding 95% CI and the p-value will be derived from the MMRM model for comparison of dupilumab against placebo at each timepoint. Note that PRQLQ-IA score (in those with history of allergic rhinitis) will only be analyzed for patients with the history of allergic rhinitis.

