1 OVERVIEW AND INVESTIGATIONAL PLAN

1.1 STUDY DESIGN AND RANDOMIZATION

EFC14153 is a multinational, multicenter, randomized, double blind, placebo-controlled, parallel group study assessing the effect of dupilumab administered subcutaneously (SC) for 52 weeks in children 6 to <12 years of age with uncontrolled persistent asthma. Patients with baseline body weight of ≤ 30 kg will be assigned dupilumab 100mg Q2W/matching placebo, and patients with weight >30 kg at baseline will be assigned dupilumab 200 mg Q2W/matching placebo. Both investigator and patients are unblinded to the dose level of dupilumab 200 mg/matching placebo or dupilumab 100 mg/matching placebo due to different volume (1.14 mL vs. 0.67 mL).

After a screening phase of 4 ± 1 weeks, patients will be centrally randomized using permuted block randomization schedule via Interactive Voice Response System/Interactive Web Response System (IVRS/IWRS) in a 2:1 randomization ratio for dupilumab and placebo. Randomization will be stratified by ICS dose level (medium, high) at screening, eosinophil count (<0.3 Giga/L versus ≥ 0.3 Giga/L) at screening and regions (Latin America: Argentina, Brazil, Colombia, Chile and Mexico; Eastern Europe: Poland, Hungary, Romania, Lithuania, Russia, Ukraine and Turkey; Western Countries: Australia, Canada, Italy, South Africa, Spain, and USA).

Approximately 402 patients will be randomized in this study with approximately 345 patients having either baseline eosinophil ≥ 0.15 Giga/L or baseline FeNO ≥ 20 ppb, and approximately 255 patients having baseline eosinophil ≥ 0.3 Giga/L. [REDACTED]

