2 STATISTICAL AND ANALYTICAL PROCEDURES

2.1 ANALYSIS ENDPOINTS

2.1.1 Demographic and baseline characteristics

The baseline value of efficacy parameters is defined as the last available value up to randomization but prior to the first dose of study medication unless otherwise specified. The baseline value of safety parameters is defined as the last available value prior to the first dose of investigational medicinal product (IMP). The baseline value of the other parameters is defined as the last available value prior to the first dose of IMP if the patient is treated, or the last available value up to randomization if the patient is not exposed to IMP.

All baseline safety and efficacy parameters (apart from those listed below) are presented along with the post-baseline summary statistics in the safety and efficacy sections ([Section 2.5](#) and [Section 2.4.4](#)).

Demographic characteristics

Demographic variables are

- Gender (Male, Female)
- Race (Caucasian/White, Black/of African descent, Asian/Oriental, American Indian or Alaska native, Native Hawaiian or other Pacific Islander, Other)
- Age in years
- Ethnicity (Hispanic, non-Hispanic)
- Region (Latin America: Argentina, Brazil, Colombia, Chile and Mexico; Eastern Europe: Poland, Hungary, Romania, Lithuania, Russia, Ukraine and Turkey; Western Countries: Australia, Canada, Italy, South Africa, Spain, and USA)
- Weight in kg (quantitative and qualitative variable: ≤ 30 , > 30 kg)
- BMI in kg/m^2 (quantitative and qualitative variable: < 20 , ≥ 20 kg/m^2)

Medical or surgical history

Medical (or surgical) history includes all the relevant medical (or surgical) history during the lifetime of the patient.

This information will be coded using the version of Medical Dictionary for Regulatory Activities (MedDRA) currently in effect at Sanofi at the time of database lock.

Comorbidity history will be summarized separately. The following comorbid diseases will be summarized.

- Atopic dermatitis history (Yes, Ongoing condition)
- Allergic conjunctivitis history (Yes, Ongoing condition)
- Allergic rhinitis history (Yes, Ongoing condition)
- Allergic conjunctivitis and/or rhinitis history (Yes, Ongoing condition)
- Chronic rhinitis history (Yes, Ongoing condition)
- Chronic sinusitis history (Yes, Ongoing condition)
- Nasal polyposis history (Yes, Ongoing condition)
- Chronic rhinitis and sinusitis with nasal polyposis
- Chronic rhinitis and sinusitis without nasal polyposis

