2.1.7 Pharmacodynamic/genomics endpoints

Serum total IgE, antigen-specific IgE, antigen-specific IgG4 panel, and Thymus and Activation-Regulated Chemokine (TARC) will all be assayed at Visit 2(Week 0), (TARC only Visit 8 (Week 12)), Visit 14 (Week 28), and EOT (Week 52).

Fractional exhaled nitric oxide (FeNO) will be analyzed using a NIOX instrument (Aerocrine AB, Solna, Sweden), or similar analyzer using a flow rate of 50 mL/s, and reported in parts per billion (ppb). This assessment should be conducted prior to spirometry and following a fast of at least 1 hour at Visit 1(Week -4±1), Visit 2 (Week 0), Visit 3 (Week 2), Visit 4 (Week 4), Visit 5 (Week 6), Visit 6 (Week 8), Visit 7 (Week 10), Visit 8 (Week 12), Visit 10 (Week 16), Visit 12 (Week 20), Visit 14 (Week 24), Visit 16 (Week 28), Visit 18 (Week 32), Visit 20 (Week 36), Visit 22 (Week 40), Visit 24 (Week 44), Visit 26 (Week 48), Visit 28 (Week 52), Visit 29 (Week 56), Visit 30(Week 60), Visit 31(Week 64).

Blood eosinophil counts from hematology assays will be collected at Visit 1(Week -4±1), Visit 2 (Week 0), Visit 8 (Week 12), Visit 14 (Week 24), Visit 20 (Week 36), Visit 28 (Week 52), Visit 31(Week 64) and early termination.

[REDACTED]

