2.3.1 Efficacy populations

The full intent-to-treat (ITT) population is defined as all randomized patients.

Type 2 inflammatory asthma phenotype population is defined as the randomized patients with baseline blood eosinophils ≥ 0.15 Giga/L or baseline FeNO ≥ 20 ppb.

Baseline blood eosinophils ≥ 0.3 Giga/L population is defined as the randomized patients with baseline blood eosinophils ≥ 0.3 Giga/L.

Baseline blood eosinophils ≥ 0.15 Giga/L population is defined as the randomized patients with baseline blood eosinophils ≥ 0.15 Giga/L.

Baseline FeNO ≥ 20 ppb population is defined as the randomized patients with baseline FeNO ≥ 20 ppb.

All efficacy endpoints will be analyzed based on both the population with a Type 2 inflammatory asthma phenotype and the population with baseline blood eosinophils ≥ 0.3 Giga/L. For selected efficacy endpoints, the analysis will be done for all four efficacy populations. For detailed analysis plan, refer to [Appendix M](#). For the analysis of primary efficacy endpoint, the testing hierarchy will start with the patients with baseline blood eosinophils ≥ 0.3 Giga/L population for the US and US reference countries; For EU and EU reference countries, the testing hierarchy will start with the Type 2 inflammatory asthma phenotype population (patients with baseline blood eosinophils ≥ 0.15 Giga/L or baseline FeNO ≥ 20 ppb). For more details about multiplicity consideration, refer to [Section 2.4.4.4](#).

Patients will be analyzed in the treatment group to which they are randomized.

For PRO endpoints which are only valid on specific subpopulations of patients, only patients within the subpopulation will be analyzed according to their randomized treatment group. Such subpopulations include patients of age ≥ 7 years old at randomization for PACQLQ(S) and patients with history of allergic rhinitis for PRQLQ-IA.

If a patient is unblinded during the study, only data obtained before the unblinding will be included in the efficacy analyses.

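### In the US primary population (baseline eosinophils at or above 0.3 Giga/L) the primary model has no term for the screening eosinophil stratum used to randomise, although that stratum can still vary there; the cost is a little precision

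*SAP*

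**What the plan says.** SAP 1.1 sets the randomisation factors: "Randomization will be stratified by ICS dose level (medium, high) at screening, eosinophil count" (below 0.3 against at or above 0.3 Giga/L), also at screening, and region. Protocol 8.4 and 11.1 agree.

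The analysis uses a different reading. SAP 2.1.1 states: "The baseline value of efficacy parameters is defined as the last available value up to randomization but prior to the first dose of study medication". SAP 2.4.6.2 takes the last value before first dose for biomarkers. Protocol 11.4.4.3 names the Visit 2 (Day 1) sample, with another pre-dose sample as fallback if that one is technically disqualified. SAP 2.1.7 says "Blood eosinophil counts from hematology assays will be collected at Visit 1" and lists Visit 2 as well, so two counts normally exist.

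SAP 2.3.1 defines the efficacy populations on baseline counts and says that "the testing hierarchy will start with the patients with baseline blood eosinophils" at or above 0.3 Giga/L for the US and its reference countries.

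In SAP 2.4.4.1 the negative binomial model for the Type 2, ≥0.15 Giga/L and full ITT populations includes baseline eosinophil category (cut at 0.3), ICS dose level and region. For the ≥0.3 Giga/L population, "the baseline eosinophil level will be removed from the model covariates". Protocol 11.4.2.1 and SAP Table 6 say the same. No screening-stratum term appears in the model text, the sample SAS code or Table 6, and no listed sensitivity analysis uses it.

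**The concern.** Dropping a constant covariate is correct. The gap is that the randomisation factor is a different variable, and restricting on the baseline count does not make it constant. A child with fewer than 300 cells/µL at screening and 300 or more at Visit 2 belongs to the US primary population but was randomised in the lower stratum.

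Region and ICS dose level both stay in that model. Eosinophil count is the only stratification factor with no term, in the population tested first in the US hierarchy (SAP Table 9). If the stratum predicts exacerbations within the restricted population, leaving it out gives up some precision. It also leaves the primary model out of step with the randomisation, which a regulatory reader may query.

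**Working it through.** **1. The plan's own figures.** Protocol 11.1 gives 402 randomised (268:134, a 2:1 ratio) with 64% at or above 300 cells/µL at baseline and 86% Type 2.
- 402 × 0.64 = 257.3, against about 255 in SAP 1.1.
- 402 × 0.86 = 345.7, against about 345.

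Both agree. The power and effect assumptions behind 402 are redacted, so they cannot be reproduced. As a formula check only, take the superseded design shown in SAP Table 1: 196 and 98 children, rates 0.5 and 1.0, dispersion 1.5, 0.9 year. The variance of the log rate ratio is the sum over arms of 1/(n × 0.9 × rate) + 1.5/n:
- 1/(196 × 0.9 × 0.5) + 1.5/196 + 1/(98 × 0.9 × 1.0) + 1.5/98 = 0.0456.
- z = ln 2/√0.0456 = 3.245; power = Φ(3.245 − 1.96) = 90%, as stated there.

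**2. How many children in the US primary population come from the lower stratum.** The documents give no visit-to-visit correlation and no share at or above 300 at screening. Assume log counts are bivariate normal with 64% at or above 300 at each visit. Then P(screening <300 given baseline ≥300) = [0.64 − P(both ≥300)]/0.64.

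| Correlation (assumed) | P(both ≥300) | Share from lower stratum | Children of 257 |
|---|---|---|---|
| 0.5 | 0.485 | 24% | 62 |
| 0.6 | 0.502 | 22% | 55 |
| 0.7 | 0.522 | 18% | 48 |
| 0.8 | 0.544 | 15% | 39 |
| 0.9 | 0.573 | 11% | 27 |

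**3. What adding the stratum changes.** Simulation with 4000 trials per scenario: N = 402, 2:1, blocks of 3 within screening eosinophils × ICS dose × region, and a negative binomial fit with log duration as offset. None of these inputs is in the current plan: correlation 0.5 or 0.8, log-rate slope of 0.25 or 0.6 per SD of underlying eosinophil level, rate ratio 0.55 or 1.0, block size, and other covariate effects. Dispersion 1.5 is from the superseded text.

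Population with baseline ≥0.3 Giga/L, without → with the stratum:

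| Correlation | Slope | Power, % (rate ratio 0.55) | Type I error, % | SE at rate ratio 0.55 |
|---|---|---|---|---|
| 0.5 | 0.25 | 67.7 → 67.9 | 6.1 → 6.4 | 0.2445 → 0.2439 |
| 0.5 | 0.6 | 66.4 → 67.0 | 7.3 → 7.1 | 0.2444 → 0.2420 |
| 0.8 | 0.25 | 67.1 → 67.3 | 5.8 → 5.9 | 0.2420 → 0.2415 |
| 0.8 | 0.6 | 67.4 → 68.6 | 6.7 → 6.7 | 0.2385 → 0.2368 |

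Power rises by 0.2 to 1.2 points. Over these and the null scenarios the SE falls by 0.2 to 1.0%. Type I error moves by at most 0.3 point, in no consistent direction. The estimated rate ratio stays at about 0.55 under both models.

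Only differences between models should be read. The absolute power is not the trial's power. The type I error above 5% comes from Wald z tests and the assumed heterogeneity, and is similar with and without the stratum. One power figure has a Monte Carlo standard error of √(0.67 × 0.33/4000) = 0.74 point, so the smaller power gains mean little singly. The fall in SE in every scenario is the steadier evidence.

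**4. Models that keep the baseline category.** In all 402 children, standing in for the Type 2 population, adding the stratum raised power from 83.4 to 83.5, 79.9 to 80.7, 83.2 to 83.4 and 80.2 to 80.6%. Replacing the baseline category with the stratum moved power by −0.3 to +0.4 point.

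**The case against.** The strongest case against is that nothing material is at stake. The US population is already restricted to high counts, which removes much of what the stratum could explain. The gain is about a point of power at best, on assumed correlations and effects. That stands, and it limits the point to a minor improvement.

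The change is also not entirely free. Protocol 11.4.2.1 fixes the covariate set, so this is a departure from the protocol. SAP section 4 says all patients have completed follow-up, so a late change to a primary model invites questions about timing. This stands too, and governs how the change is made. It is not a bar: SAP Table 3 already records a change to the protocol's covariates for the key secondary model.

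Baseline is not always Visit 2: a child without a usable Visit 2 count keeps an earlier one, and for that child stratum and baseline would normally agree. This lowers the share in the table somewhat but does not make the stratum constant.

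Two stronger readings are tempting. A reader might infer that every primary model omits a stratification factor. The documents do not support that: the Type 2, ≥0.15 Giga/L and ITT models include eosinophils at the same cut, measured closer to dosing, and swapping in the stratum brings no consistent gain. A reader might also infer that the primary test is biased or has the wrong type I error. Nothing in the documents or the simulation shows this.

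**Conclusion.** The point holds for one model. In the baseline ≥0.3 Giga/L population the primary negative binomial model omits a factor the trial randomises on, and that factor can vary there. The omission can be read directly from the documents. The number of children affected (11 to 24%) and the gain (0.2 to 1.2 points of power, SE 0.2 to 1.0% lower) depend on assumed visit-to-visit correlations and prognostic effects. It is a small, inexpensive improvement in precision and in consistency with the randomisation, and it does not call the validity of the primary analysis into question.

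It should not be extended to the MMRM models or to the high-ICS subsets lower in the hierarchy. Neither was tested, and sparse cells in those subsets could cause the convergence trouble that SAP 2.4.4.1 already provides for.

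**What to change.** Before unblinding, add the screening eosinophil stratum (<300, ≥300 cells/µL) recorded in the randomisation system as a binary covariate in the negative binomial model for the baseline ≥0.3 Giga/L population. Carry it through the model text, the sample code and Table 6, and record it in SAP Table 3 as a change from Protocol 11.4.2.1. State which value is used when the recorded stratum differs from the actual screening count, since SAP 2.2.1 expects some stratification errors. If unblinding has occurred, leave the primary model as it is and report the added term as a labelled sensitivity analysis.

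In the Type 2, ≥0.15 Giga/L and ITT models keep the baseline category; adding the stratum there is optional.

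The cost is one degree of freedom, a short SAP edit and no new data. The same edit can reconcile SAP 2.5.6, which describes stratification by country, with SAP 1.1 and Protocol 11.1, which give region.
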